2. OVERALL SYNOPSIS OF THE CLINICAL INVESTIGATION

Clinical investigation title:	Validation of the performance of the electrocardiogram (ECG) function of the INVSENSOR00057
Study objective(s):	The objective of this study is to validate the performance of the electrocardiogram (ECG) function of the Masimo INVSENSOR00057 against contemporaneous measurements from reference 12-lead ECG gold standard.
Study device(s):	
Masimo devices:
 
• Masimo INVSENSOR00057 – Investigational 
Comparators:
 
• FDA-approved 12-lead electrocardiogram (ECG) electrodes and monitors 
Research Equipment:
 
• Data collection research equipment (e.g., laptops, automated data collection software, data collection application, or comparable)
Number of subjects:	
Inclusion criteria:	
• Subject is 22 years of age or older.• Subject is comfortable to read and communicate in English*.• Subject belongs to one of the two groups:
○ Subjects without prior arrhythmia diagnosis presenting in normal sinus rhythm (Group 1)○ Subjects with history of paroxysmal or persistent atrial fibrillation presenting in atrial fibrillation (Group 2). 
*This is to ensure the subject can provide informed consent (as Masimo INVSENSOR00057 ECG study materials are currently available in English only) and can comply with study procedures.

Exclusion criteria:	
• Subjects who are physically unable to wear a wristwatch.• Subjects whose skin is not intact (e.g., has open wounds, has inflamed tattoos or piercings, has visible healing wounds) in or at the vicinity of the device placement site.• Subjects with an implantable defibrillator or cardiac pacing device.• Subjects with a skin condition which would preclude proper ECG electrode placement.• Subjects with known allergic reactions to adhesive tapes or ECG gel.• Subjects previously diagnosed with lethal cardiac arrhythmia, determined by the investigator.• Subjects not suitable for the investigation at the discretion of the investigator or the clinical team.

Study Title: Validation of the performance of the electrocardiogram (ECG) function of the Masimo INVSENSOR00057

Groups and Randomization:	
Two groups of normal sinus rhythm and atrial fibrillation, where subjects are assigned to each group based on the clinical interpretation of the reference 12-lead ECG results. To ensure equal representation of two groups, a targeted enrollment approach will be taken at enrollment sites, where subjects with no known arrhythmia (normal sinus rhythm) will be recruited at Masimo Clinical Laboratory and subjects with known diagnosis of atrial fibrillation will be recruited at external sites.
 
• NSR - Subjects with no arrhythmia (normal sinus rhythm) based on the clinical interpretation of the reference 12-lead ECG results.• AFib - Subjects with known diagnosis of atrial fibrillation based on the clinical interpretation of the reference 12-lead ECG results.
Duration of the clinical investigation:	
The study is anticipated to require ~ 3 months to complete. Subject participation in the study will be approximately 30 minutes.

Study endpoint(s):	
Primary: Evaluate the diagnostic performance of ECG rhythm classification and waveform characteristics.
 
• Sensitivity and specificity of the automatic classification of atrial fibrillation (AFib) and normal sinus rhythm (NSR) by the single-lead ECG module of INVSENSOR00057 against clinical interpretation of a reference 12-lead ECG.• [REDACTED]• [REDACTED]• [REDACTED]

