An atrial fibrillation ECG classification will indicate that ECG shows signs of irregular heartbeat. Atrial fibrillation is the most common pathologic cardiac arrhythmia. Masimo INVSENSOR00057 can detect signs of atrial fibrillation between heart rates of 50 to 150 bpm. Atrial fibrillation can often be accompanied by a rapid heart rate. Subjects who have not been previously diagnosed with atrial fibrillation and consistently receive this result or subjects who are not feeling well should consult with their healthcare provider. The resulting output does not guarantee the presence or absence of atrial fibrillation or other arrhythmias.

- Inconclusive

An Inconclusive ECG classification indicates that the ECG recording could not be classified, which may be due to a number of reasons such as other arrhythmias, pacing, or heart conditions that Masimo INVSENSOR00057

Study Title: Validation of the performance of the electrocardiogram (ECG) function of the Masimo INVSENSOR00057

is not designed to detect. It is recommended to repeat the measurement in a few minutes for subjects who get this result. An inconclusive classification does not indicate the presence or absence of any arrhythmias (including AFib) or other heart conditions. Subjects who consistently receive this result should follow up with their healthcare provider, particularly if they are feeling unwell.

- Noise

This classification of the ECG means the ECG waveform quality and performance were compromised and the device cannot report any measurements from the ECG.

INVSENSOR00057 Heart Rate Classification:

- Low Heart Rate

A low heart rate ECG classification will indicate a heart rate lower than 50 bpm, which can be commonly due to benign causes such as certain medication effects, or a normal finding during rest in particular among well-conditioned athletes or other cardiovascularly-fit individuals. However, subjects who are not feeling well should follow up with their healthcare provider as sometimes very low heart rates can indicate an underlying cardiovascular condition.

- High Heart Rate

A high heart rate ECG classification will indicate heart rates greater than 100 bpm, which can be due to exercise, stress, the presence of cardiac arrhythmia, or consumption of alcohol, stimulants or caffeinated drinks. Subjects who are not feeling well should follow up with their healthcare provider.

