7. DESIGN OF THE CLINICAL INVESTIGATION

7.1. General

This is a prospective validation study of Masimo INVSENSOR00057 ECG function (see [Appendix I](#) for a study workflow) in a mix of subjects with and without a diagnosis of AFib. Enrolled subjects will receive [REDACTED]

[REDACTED] on Masimo INVSENSOR00057. [REDACTED]

[REDACTED] Clinician interpretation of reference 12-lead ECG classification will be used in classifying subjects to rhythm cohorts and establish the basis for analysis of subject data with respect to study endpoints.

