7.5. Subjects

7.5.1. Inclusion Criteria

- Subject is 22 years of age or older.
- Subject is comfortable to read and communicate in English*.
- Subject belongs to one of the two groups:
 - Subjects without prior arrhythmia diagnosis presenting in normal sinus rhythm (Group 1)
 - Subjections with history of paroxysmal or persistent atrial fibrillation presenting in atrial fibrillation (Group 2).

*This is to ensure the subject can provide informed consent (as Masimo INVSENSOR00057 ECG study materials are currently available in English only) and can comply with study procedures.

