7.6. Study Procedures

7.6.1. Subject Recruitment and Pre-screening

Subjects with no known arrhythmia (normal sinus rhythm) will be recruited at [REDACTED] and subjects with known diagnosis of atrial fibrillation will be recruited at external sites from medical clinics or cardiology offices. Subjects in the AFib cohort may have paroxysmal, persistent, or permanent forms of AFib, and will be determined by the referring cardiologist to be in atrial fibrillation at the time of routine office visit.

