7.6.3.2. Data Analysis

The digital pdf ECG data will be downloaded and provided to Masimo. Three independent board-certified cardiologists will be tasked with rhythm classification and [REDACTED]

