8.1. Classification Accuracy Calculations

8.1.1. Data Analysis

Classification accuracy will be measured on all measurements where both the INVSENSOR00057 and the 12-lead reference ECG provided a classification of either AFib or NSR. (This incidence rate of Inconclusive and Noise outcomes on the INVSENSOR00057 will be evaluated separately.) Sensitivity is the probability that the diagnostic test is positive for the disease, given that the subject actually has AFib, while specificity is the probability that the diagnostic test is negative, given that the subject does not have AFib (or conversely, has NSR).

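### Does Section 8.1.1 define specificity for a wider population than the study recruits?

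*Combined protocol and SAP*

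**What the plan says.** Section 8.1.1 contains two statements that have to be read together. The analysis set is "all measurements where both the INVSENSOR00057 and the 12-lead reference ECG provided a classification of either AFib or NSR". The definition is that "specificity is the probability that the diagnostic test is negative, given that the subject does not have AFib (or conversely, has NSR". Inconclusive and Noise outputs from the device are evaluated separately.

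The non-AFib group is described elsewhere. Section 7.5.1 admits "Subjects without prior arrhythmia diagnosis presenting in normal sinus rhythm (Group 1". The synopsis, under Groups and Randomization, says that "subjects with no known arrhythmia (normal sinus rhythm) will be recruited at Masimo Clinical Laboratory and subjects with known diagnosis of atrial fibrillation" at external sites, which places recruitment of the non-AFib group at one named laboratory; Section 7.6.1 takes AFib subjects from external medical clinics or cardiology offices.

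On who decides the rhythm, Section 7.1 says "Clinician interpretation of reference 12-lead ECG classification will be used in classifying subjects to rhythm cohorts", and the synopsis labels both cohorts by the same reading. Before that, under Section 7.6.1, AFib-cohort subjects "will be determined by the referring cardiologist to be in atrial fibrillation at the time of routine office visit". Section 7.6.3.2 adds: "Three independent board-certified cardiologists will be tasked with rhythm classification". The rest of that sentence is blacked out.

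**The concern.** Not having AFib and being in NSR are different conditions in general. Section 3 itself lists reasons for an Inconclusive result "such as other arrhythmias, pacing, or heart conditions", which are neither AFib nor NSR. If Section 8.1.1 really meant anyone without AFib, the recruited sample could not support it.

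The three descriptions also seem to disagree. The definition speaks of subjects without AFib, the cohort rule speaks of the reference reading, and eligibility speaks of subjects with no earlier arrhythmia diagnosis. They part company for a Group 2 subject, possibly with paroxysmal AFib, whom the referring cardiologist judged to be in AFib but whose 12-lead ECG is later read as NSR. The analysis rule would count that subject towards specificity, although the subject meets neither group's eligibility description.

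At stake would be who enters the denominator of a primary endpoint, and how far the resulting figure may be generalised.

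**Working it through.** **1. Definition against analysis set.** Take every possible reference reading and apply the opening rule of Section 8.1.1:

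| Reference reading | In the accuracy set? | Counts towards |
|---|---|---|
| AFib | yes, if the device gave AFib or NSR | sensitivity |
| NSR | yes, if the device gave AFib or NSR | specificity |
| any other rhythm | no | neither |
| unreadable | no (Section 8, opening text) | neither |

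Only two reference states survive, so inside this set the complement of AFib is exactly NSR. The parenthesis in the definition is therefore correct where it is applied.

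**2. What the rule avoids.** If other rhythms were in the denominator, specificity would be (1 - w) × Sp_NSR + w × Sp_other, where w is the share of non-AFib subjects in another rhythm. With assumed values Sp_NSR = 0.98, w = 0.10 and Sp_other = 0.50 to 0.90, this gives 0.882 + 0.050 = 0.932 to 0.882 + 0.090 = 0.972. The two quantities can differ, but only the NSR one is planned. The list in Section 3 concerns causes of an Inconclusive output, which is outside the accuracy set; pacing devices are also an exclusion under Section 7.5.2.

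**3. The discordant Group 2 subject.** Section 7.5.1 requires Group 2 to present in AFib, and Section 7.5.4 counts as enrolled only those who meet all inclusion criteria. If the reference nevertheless reads NSR, the synopsis and Sections 7.1 and 8.1.1 point the same way: the reference reading decides.

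**4. Size of that case.** The documents give no counts and the sample size is redacted, so all inputs here are assumed. Let Group 1 have n subjects with x false positives, and add k Group 2 subjects read as NSR with f false positives among them. Specificity becomes (n - x + k - f)/(n + k).

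| Group 1 alone | k, f | Combined | Change (points) |
|---|---|---|---|
| 197/200 = 98.50% | 10, 0 | 207/210 = 98.57% | +0.07 |
| | 5, 2 | 200/205 = 97.56% | -0.94 |
| | 10, 4 | 203/210 = 96.67% | -1.83 |
| | 4, 4 | 197/204 = 96.57% | -1.93 |
| 98/100 = 98.00% | 10, 0 | 108/110 = 98.18% | +0.18 |
| | 4, 4 | 98/104 = 94.23% | -3.77 |
| 296/300 = 98.67% | 10, 0 | 306/310 = 98.71% | +0.04 |
| | 4, 4 | 296/304 = 97.37% | -1.30 |

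With k = 0, or with the same false-positive rate as Group 1 (f/k = x/n), the change is zero. Each lower extreme needs every added subject to be a false positive. Even so, 96.57% lies inside the exact (Clopper-Pearson) 95% interval for 197/200, 95.68% to 99.69%, and 94.23% lies inside that for 98/100, 92.96% to 99.76%.

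**The case for a change.** The best case for a change is this. Section 5.1 says the study supports a regulatory submission, and Section 3 describes a consumer product whose users are not confined to people without an arrhythmia history. The visible endpoint wording repeats neither the no-prior-arrhythmia limit nor the single source. Rhythm group and recruitment source coincide by design. A few words now would cost nothing and would remove any later choice about discordant subjects.

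Parts of this stand. The parenthesis in Section 8.1.1 is loose out of context, and the NSR sample is narrow. But eligibility, cohort assignment and analysis set are three layers of one protocol, not rival definitions, and the plan already names the NSR group in the synopsis and in Section 7.5.1. The overlap of group and source limits generalisation. It does not enter the calculation, because sensitivity and specificity are each proportions within one reference group, not a comparison between groups.

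Nor is a later choice left open in the visible text, since the reference reading decides. A more detailed rule may lie in the blacked-out parts of Sections 7.1, 7.6.3.2 and 8.1.2 or in the text missing between Sections 7.1 and 7.3, so its absence cannot be counted against the plan.

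The natural edits also pull against each other. Counting Group 2 subjects read as NSR, while stating that the conclusion covers only people without a prior arrhythmia diagnosis from one laboratory, would write a mismatch into the plan. Specificity tables by age band would be imprecise in small bands (exact lower limit 83.2% for 20/20, 91.2% for 40/40) and would leave the single source as it is.

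**Conclusion.** The concern does not hold as a defect. Followed as written, the plan gives a sound specificity against NSR on the reference ECG, and rewording the definition would leave both the rule and the number unchanged. The only case with any numerical effect is the Group 2 subject read as NSR. Under the assumed counts above, the change runs from -1.93 to +0.07 points with 200 in Group 1 (-3.77 to +0.18 with 100, -1.30 to +0.04 with 300), and it may well be zero. Whether specificity differs in people unlike the recruited sample cannot be derived from the documents, and no direction is claimed.

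What remains is ordinary reporting: describe where the NSR sample came from, give the number of any Group 2 subjects counted as NSR, and call the result one for people without a prior arrhythmia diagnosis only if the Group 1 figure is meant. An analyst would do this without a change to the plan. The conclusion rests on the visible text; the single-laboratory point rests on the synopsis alone, because the site is blacked out in Section 7.6.1.

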3. DESCRIPTION OF THE STUDY DEVICE

As a leader in hospital pulse oximetry, Masimo brings over 30 years of innovation and breakthrough advances in noninvasive blood parameter monitoring to miniaturize its monitoring technology and integrate it into a wristwatch. Masimo INVSENSOR00057 [REDACTED] offers accurate, continuous health data and actionable health insights in a personal, lifestyle-friendly wristwatch. Masimo INVSENSOR00057 provides a variety of physiological data for consumers wanting to make better informed health and lifestyle decisions, improve their fitness, or track their health data. These parameters include hydration index (Hi), oxygen saturation level (SpO₂), pulse rate (PR), pulse rate variability (PRV), respiration rate (RRp[®]), pleth variability index (PVi), perfusion index (Pi). Additionally, Masimo INVSENSOR00057 is equipped with an ECG module, which captures the electrical signals of the heartbeat and informs user of potential atrial fibrillation (AFib) and their heart rate (HR). This validation study pertains to the ECG module of the Masimo INVSENSOR00057.

Study Title: Validation of the performance of the electrocardiogram (ECG) function of the Masimo INVSENSOR00057

As shown in Figure 1, the Masimo INVSENSOR00057 ECG

Figure 2).

A.

B.

Figure 1. Overview of Masimo INVSENSOR00057. A. Front and Back view of Masimo INVSENSOR00057 B. [REDACTED] Masimo INVSENSOR00057 can be paired with [REDACTED] devices to provide users with important health data.

With each ECG spot check, Masimo INVSENSOR00057 provides the average heart rate, rhythm classification, and a description of the classification as detailed below.

INVSENSOR00057 Rhythm Classification:

- Normal Sinus Rhythm

A Normal Sinus Rhythm ECG classification will indicate that ECG shows signs of a normal regular heartbeat with heart rates of 50 to 100 bpm. The ECG output of normal sinus rhythm only applies to the duration of the spot-check measurement and does not fully exclude cardiac arrhythmias. Subjects who are not feeling well should follow up with their healthcare provider.

- Atrial Fibrillation

An atrial fibrillation ECG classification will indicate that ECG shows signs of irregular heartbeat. Atrial fibrillation is the most common pathologic cardiac arrhythmia. Masimo INVSENSOR00057 can detect signs of atrial fibrillation between heart rates of 50 to 150 bpm. Atrial fibrillation can often be accompanied by a rapid heart rate. Subjects who have not been previously diagnosed with atrial fibrillation and consistently receive this result or subjects who are not feeling well should consult with their healthcare provider. The resulting output does not guarantee the presence or absence of atrial fibrillation or other arrhythmias.

- Inconclusive

An Inconclusive ECG classification indicates that the ECG recording could not be classified, which may be due to a number of reasons such as other arrhythmias, pacing, or heart conditions that Masimo INVSENSOR00057

Study Title: Validation of the performance of the electrocardiogram (ECG) function of the Masimo INVSENSOR00057

is not designed to detect. It is recommended to repeat the measurement in a few minutes for subjects who get this result. An inconclusive classification does not indicate the presence or absence of any arrhythmias (including AFib) or other heart conditions. Subjects who consistently receive this result should follow up with their healthcare provider, particularly if they are feeling unwell.

- Noise

This classification of the ECG means the ECG waveform quality and performance were compromised and the device cannot report any measurements from the ECG.

INVSENSOR00057 Heart Rate Classification:

- Low Heart Rate

A low heart rate ECG classification will indicate a heart rate lower than 50 bpm, which can be commonly due to benign causes such as certain medication effects, or a normal finding during rest in particular among well-conditioned athletes or other cardiovascularly-fit individuals. However, subjects who are not feeling well should follow up with their healthcare provider as sometimes very low heart rates can indicate an underlying cardiovascular condition.

- High Heart Rate

A high heart rate ECG classification will indicate heart rates greater than 100 bpm, which can be due to exercise, stress, the presence of cardiac arrhythmia, or consumption of alcohol, stimulants or caffeinated drinks. Subjects who are not feeling well should follow up with their healthcare provider.

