8. STATISTICAL DESIGN AND ANALYSIS

The study objective is to evaluate the performance of the INVSENSOR00057 rhythm classification and waveform characteristics relative to a 12-lead ECG. The INVSENSOR00057 evaluates a 30 second duration, single lead, ECG waveform measurement. One of four possible outcomes for each measurement per Table 8a.

Outcome	Description
AFib	Waveform is classified as atrial fibrillation
NSR	Waveform is classified as Normal Sinus Rhythm
Inconclusive	INVSENSOR00057 cannot determine the rhythm classification
Noise	INVSENSOR00057 has determined that the waveform is too noisy and does not represent a physiological signal

CLINICAL INVESTIGATION PLAN

Study Title: Validation of the performance of the electrocardiogram (ECG) function of the Masimo INVSENSOR00057

Data from subjects where reference 12-lead ECG did not provide readable ECG waveforms (as assessed by medical personnel) will be excluded from the primary analysis.

[figure not shown]

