8.3.2. Sample size

It is not possible to control the subject heart rate during this study, so it is not possible to validate the entire range of heart rate [REDACTED]. Further, the heart rate of Afib patients is ill defined, so a comparison in this cohort is not possible.

Therefore, the data collected in this study for the NSR cohort only will be used as a convenience sample of the INVSENSOR00057 heart rate output.

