8.3.3. Acceptance Criteria

$A_{RMSE} \leq 5$ bpm over the clinical range found in the normal sinus rhythm cohort.

The INVSENSOR00057 full range of [REDACTED] is validated separately using ECG simulators.

Study Title: Validation of the performance of the electrocardiogram (ECG) function of the Masimo INVSENSOR00057

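### If the device withholds NSR above 100 bpm, the 8.1.1 sensitivity cannot register a missed AFib at 101–150 bpm, so the pooled figure needs an all-recordings, rate-banded companion

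*Combined protocol and SAP*

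**What the plan says.** Section 3 gives the two rhythm outputs different rate ranges. The NSR output indicates "signs of a normal regular heartbeat with heart rates of 50 to 100 bpm". For the other output, "Masimo INVSENSOR00057 can detect signs of atrial fibrillation between heart rates of 50 to 150 bpm". A separate heart-rate label sits beside the rhythm result: "A high heart rate ECG classification will indicate heart rates greater than 100 bpm".

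Section 8 lists what the device can return: "One of four possible outcomes for each measurement per Table 8a", namely AFib, NSR, Inconclusive or Noise. The table attaches no rate limit to any of them.

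Section 8.1.1 fixes the analysis set: "Classification accuracy will be measured on all measurements where both the INVSENSOR00057 and the 12-lead reference ECG provided a classification of either AFib or NSR". The incidence of Inconclusive and Noise is to be evaluated separately.

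On heart rate at entry, the eligibility criteria in 7.5 set no limit, and 7.6.1 recruits AFib subjects who are in AFib at a routine office visit. Section 8.3.2 adds: "It is not possible to control the subject heart rate during this study". For heart-rate accuracy the plan limits its claim accordingly. The criterion in 8.3.3 applies "over the clinical range found in the normal sinus rhythm cohort", and the full range is covered separately with simulators.

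**The concern.** Under 8.1.1 a false negative is a recording that the reference calls AFib and the device calls NSR. If NSR is not an available output above 100 bpm, no false negative can arise at a device rate of 101–150 bpm. A reference-AFib recording there is either a true positive or is left out. The 8.1.1 sensitivity in that band then carries no information about detection, yet those recordings are pooled with the 50–100 bpm recordings, where a miss can be counted.

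This sensitivity is a primary endpoint in a study meant to support a regulatory submission, and section 3 itself says that AFib often comes with a fast rate. A reader could take one pooled figure as evidence for detection over 50–150 bpm, when the estimator is almost insensitive to performance in the upper half of that range. Two samples with different shares of fast AFib would also give different pooled sensitivities for the same device.

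**Working it through.** The visible text gives no sensitivity, sample size or interval width to reproduce; those figures are redacted. The check is therefore structural, followed by an illustration on assumed inputs.

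**Step 1: outcomes available.** Apply the section 3 ranges as hard limits on the device's own rate, then the 8.1.1 rule:

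| Device-measured rate | Outputs available | A reference-AFib recording is |
|---|---|---|
| below 50 bpm | Inconclusive, Noise | dropped |
| 50–100 bpm | AFib, NSR, Inconclusive, Noise | true positive, false negative or dropped |
| 101–150 bpm | AFib, Inconclusive, Noise | true positive or dropped |
| above 150 bpm | Inconclusive, Noise | dropped |

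In the third row, sensitivity = TP/(TP + 0) = 100% whenever at least one recording is called AFib.

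**Step 2: pooled sensitivity.** Let f be the share of AFib recordings at 101–150 bpm (the rest at 50–100 bpm), s the sensitivity at 50–100 bpm with every recording there classified, and d the share of the fast band called AFib. Then

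pooled = [(1−f)s + fd] / [(1−f) + fd], and pooled − s = fd(1−s) / [(1−f) + fd].

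The difference is never negative, so the pooled figure cannot fall below s. It is zero only if s = 1 or no fast recording is called AFib (fd = 0).

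**Step 3: illustration.** Assume d = 0.80 (20% of fast AFib unclassified). None of these inputs is in the documents.

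| f | pooled, s = 90% | AFib calls / all | pooled, s = 95% | AFib calls / all |
|---|---|---|---|---|
| 10% | 89/98 = 90.8% | 89.0% | 93.5/98 = 95.4% | 93.5% |
| 20% | 88/96 = 91.7% | 88.0% | 92/96 = 95.8% | 92.0% |
| 30% | 87/94 = 92.6% | 87.0% | 90.5/94 = 96.3% | 90.5% |
| 40% | 86/92 = 93.5% | 86.0% | 89/92 = 96.7% | 89.0% |

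The excess over s runs from 0.4 points (95.4 − 95) to 3.5 points (93.5 − 90). As f rises, the pooled figure goes up while the share of AFib recordings called AFib goes down. With s = 98% the excess is smaller: 96.2/98 − 98% = 0.2 points at f = 10%, and 90.8/92 − 98% = 0.7 points at f = 40%.

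**Step 4: response to poor fast-rate detection.** Take f = 30% and s = 90%.

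| d | pooled | AFib calls / all |
|---|---|---|
| 100% | 93/100 = 93.0% | 93% |
| 50% | 78/85 = 91.8% | 78% |
| 10% | 66/73 = 90.4% | 66% |

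Detection of fast AFib falls by 90 points and the pooled sensitivity moves by 2.6.

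**Step 5: device rate versus 12-lead rate.** A recording above 100 bpm on the 12-lead could be measured at or below 100 bpm by the device and called NSR. With 90% detection in the fast band, and 5% or 20% of the misses returned as NSR (assumed), sensitivity by 12-lead rate is 0.9/(0.9 + 0.1×0.05) = 99.4% or 0.9/(0.9 + 0.1×0.20) = 97.8%. That is near the ceiling, but not exactly 100%.

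**The case against.** The strongest reply is that the hard limit is inferred. Section 3 is a description of what the user sees. It does not say that NSR is returned only at 50–100 bpm, Table 8a has no rate limit, the high-rate label is a separate output, and the reasons given for Inconclusive do not mention rate. This stands. A reader might infer that the documents establish the impossibility of a false negative in fast AFib; they do not, and the point is conditional on the sponsor's confirmation.

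A reader might also infer that the misses are hidden altogether. They are not: 8.1.1 evaluates Inconclusive and Noise separately. But the visible text does not break that rate down by reference rhythm or heart rate, so misses in fast AFib would be mixed with every other unclassified recording.

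Nor is a split by rate the only remedy. The effect arises because 8.1.1 drops unclassified recordings, and putting all readable reference-AFib recordings in the denominator also corrects the pooled figure. The rate split adds where the misses lie. Nor is all of the pooled excess an artefact: at d = 100% the excess is real, since fast AFib is then truly better detected.

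Two further limits stand. Section 8.3.2 calls heart rate in AFib ill defined, so any banding is approximate. And three primary-endpoint bullets, the rest of 8.1.2 and all of 8.2 are not visible, so a rate range or an analysis of unclassified results may already exist there. The visible text therefore does not support a claim that the plan lacks them. What remains untouched is the 8.1.1 rule itself, which is fully visible.

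**Conclusion.** The point holds in conditional form. If the study algorithm enforces the section 3 ranges, the 8.1.1 sensitivity is 100% at a device-measured rate of 101–150 bpm whatever the detection rate, provided anything there is called AFib. It is close to 100% by 12-lead rate, and the pooled sensitivity is bounded below by the 50–100 bpm figure.

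The bound follows from the rule; the size does not. The 0.4 to 3.5 point excess rests on assumed inputs: 20% of fast AFib unclassified, nothing unclassified at 50–100 bpm, a fast share of 10–40%, and 90–95% sensitivity at 50–100 bpm. Higher sensitivity in the lower band shrinks it. If the device can return NSR above 100 bpm, the band can fail and this particular problem goes away. What is then left is the general effect of excluding Inconclusive and Noise.

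This is a reason to add to the reporting, not to discard the 8.1.1 estimate.

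**What to change.** First, have the sponsor state beside Table 8a which rhythm output the study algorithm gives for a regular-looking recording above 100 bpm.

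Keep the 8.1.1 estimate, and add to 8.1.1:

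- (a) AFib calls divided by all readable reference-AFib recordings, with Inconclusive and Noise counted as not detected, overall and by rate band (50–100, 101–150, and outside 50–150 bpm). Use the device-measured rate where available and the 12-lead ventricular rate otherwise; section 3 says a Noise result carries no device measurements, so those recordings need the 12-lead rate. Show which source was used.
- (b) The AFib-versus-NSR sensitivity for the 50–100 bpm band.
- (c) The heart-rate range observed in the AFib recordings, with the conclusion on AFib detection limited to that range, as 8.3.3 already does for heart-rate accuracy.

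If redacted text already contains any of these, a cross-reference in 8.1.1 is enough. The cost is SAP wording and one extra table from recordings already planned, with no new subjects or procedures. The downsides are that the all-recordings figure may be lower than the 8.1.1 figure, and that the 101–150 bpm band may be small and its estimate imprecise.
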